2.11.1.7. Appetite regulation

Roth and colleagues recently analyzed the gastrointestinal hormones ghrelin and peptide YY and brainderived neurotrophic factor and their effect on satiety regulation in patients with childhood craniopharyngioma and hypothalamic obesity [188, 189]. Their findings support the hypothesis that reduced ghrelin secretion and impaired postprandial suppression of ghrelin in patients with childhood craniopharyngioma and severe hypothalamic obesity leads to disturbed regulation of appetite and satiety. Peptide YY serum concentrations did not differ between normal weight, obese, and severely obese patients with childhood craniopharyngioma. A possible pathogenic role of peripheral α -melanocyte-stimulating hormone in childhood craniopharyngioma obesity has also been reported [190].

Hoffmann *et al.* [191] analysed eating disorders and eating behaviour in 101 survivors of childhoodonset craniopharyngioma and 85 BMI-matched healthy controls. Severely obese patients (BMI >+8 SD; n=9) presented with pathological eating behaviours and more weight problems and eating disorders, as compared to obese (BMI +3 to +8 SD; n=44) and normal or overweight patients (BMI <+3 SD; n=48). However, childhood-onset craniopharyngioma patients with different degree of obesity showed similar or even less pathological findings as compared to BMI-matched normal controls. Hoffmann *et al.* conclude that the observed eating disorders are not disease-specific for childhood-onset craniopharyngioma.

Roth *et al.* [192] assessed pre- and post-meal responses to visual food cues in childhood-onset adamantinomatous craniopharyngioma patients' brain regions of interest using functional magnetic resonance imaging (fMRI). Following a test meal, BMI-matched controls showed suppression of activation by high-calorie food cues while childhood-onset craniopharyngioma patients showed trends toward higher activation. These findings support the hypothesis that perception of food cues especially after food intake may be altered in childhood-onset craniopharyngioma patients with hypothalamic obesity.

Even though hypothalamic obesity is a frequent sequela in childhood-onset adamantinomatous craniopharyngioma [188], also diencephalic syndrome leading to severe weight loss and cachexia can occur as a rare hypothalamic disturbance of body composition in childhood-onset craniopharyngioma [193, 194]. Hoffmann *et al.* [194] analysed the incidence of diencephalic syndrome, its clinical manifestations before and after diagnosis of childhood-onset craniopharyngioma, and outcome in 485 patients recruited in the German childhood craniopharyngioma registry. Only 4.3% of all childhood-onset craniopharyngioma patients presented with low weight (BMI <-2 SD) at time of diagnosis. Initial significant differences between patients with low weight at the time of diagnosis and normal weight patients at diagnosis are usually observed at 5 yrs of age. Within the first two yrs after diagnosis of childhood-onset craniopharyngiome patients and normal weight patients converge to a similar level. Hoffmann *et al.* concluded from their analysis of patients' histories that diencephalic syndrome at the time of diagnosis does not preclude subsequent weight gain caused by a childhood-onset craniopharyngioma with hypothalamic involvement.

2.11.1.8. Pharmacological treatment of hypothalamic obesity

Due to disturbances in energy expenditure, central sympathetic output, and appetite-regulation, craniopharyngioma patients with hypothalamic obesity typically develop morbid obesity that is mainly unresponsive to conventional lifestyle modifications (diet and exercise) for regulating BMI. Based on impairment of sympathoadrenal activation and epinephrine production manifesting as a reduced hormonal response to hypoglycemia, treating this disorder with amphetamine derivatives has been suggested [195, 196]. Use of dextroamphetamine intervention starting 10 month post-surgical and lasting 24 month was shown to diminish continuous weight gain and to stabilize BMI [180]; importantly, spontaneous physical activity increased significantly. Even shorter periods of dextroamphetamine treatment have caused a subjective improvement in daytime sleepiness [197]. Also, Elfers *et al.*

observed beneficial effects of central stimulating agents (particularly methylphenidate) on weight development in craniopharyngioma patients [198].

Craniopharyngioma patients with hypothalamic obesity have a so-called parasympathetic predominance of the autonomic nervous system induced by vagal activation, manifesting as daytime sleepiness, reduced body temperature and lowering of heart rate [199]. Parasympathetic stimulation causes insulin secretion by way of direct activation of β -cells as well as promoting adipogenesis. As insulin is an anabolic hormone, it has been suggested to be an important driver of weight gain in hypothalamic obesity. Octreotide is a somatostatin analogue and thus causes reduction in insulin secretion. Lustig and colleagues used octreotide in a double blind randomized controlled study in children with hypothalamic obesity and demonstrated moderate reductions in weight gain [183]. The authors showed that insulin levels during a proof-of-concept oral glucose tolerance test decreased without leading to major changes in glucose tolerance. This study was followed by a larger trial performed using octreotide LAR (long-acting repeatable) in 60 patients with cranial surgical interventions that led to hypothalamic obesity [200]. This 6- month intervention showed no efficacy in changing BMI and the open label segment of this study was terminated earlier than planned due to an increased risk of gallstone formation.

Zoicas *et al.* [201] treated 8 adult patients (6 craniopharyngioma) with hypothalamic obesity with GLP-1 analogues and observed a substantial and sustained weight loss associated with improvements in metabolic and cardiovascular risk profiles.

Daubenbüchel et al. [202] recently reported that craniopharyngioma patients are able to produce and secrete the hormone oxytocin, even when pituitary and hypothalamic structures were damaged. However, patients with hypothalamic damage grade 1, which involves damage only to the anterior hypothalamic areas, presented with a lower fasting level of oxytocin. In addition, changes in oxytocin levels before and after standardized breakfast correlated with BMI, demonstrating that craniopharyngioma patients with hypothalamic obesity show less variation in oxytocin secretion due to nutrition. Accordingly, the authors speculate that oxytocin supplementation might be a therapeutic option in craniopharyngioma patients with hypothalamic obesity and/or neurobehavioral deficits due to specific hypothalamic damage in the anterior hypothalamic area. Hoffmann et al. reported on first preliminary results of a small pilot study testing this hypothesis by single nasal oxytocin application in 11 craniopharyngioma patients [203]. All patients presented with detectable levels of oxytocin before administration. Nasal administration of oxytocin was well tolerated and resulted in increased oxytocin concentrations in saliva and urine. After oxytocin administration, craniopharyngioma patients with postsurgical lesions limited to the anterior hypothalamus area showed improvements in emotional identifications compared to craniopharyngioma patients with lesions of anterior and posterior hypothalamic areas. Focusing on correct assignments to positive and negative emotion categories, craniopharyngioma patients improved assignment to negative emotions.

Up to now, there are only rare case reports on long-term effects of oxytocin treatment in craniopharyngioma reporting on parent-observed neuro-behavioral and pro-social improvements after 22 month of treatment [204] and in a second case on weight loss and reduced hyperphagia due to oxytocin therapy (10 weeks) followed by combined therapy with oxytocin and naltraxone treatment over a 38 weeks period [204].

A multicenter clinical trial titled "Intranasal Oxytocin to Promote Weight Loss in Children, Adolescents, and Adults With Brain Tumors and Hypothalamic Obesity Syndrome" (ClinicalTrials.gov Identifier: NCT 02849743 [205]) is currently recruiting patients for randomized testing if oxytocin, delivered by nasal spray, will promote weight loss in children, adolescents, and adults with hypothalamic obesity as compared to a placebo.

2.11.1.9. Bariatric treatment of hypothalamic obesity

Initial experiences with bariatric surgery in severely obese childhood craniopharyngioma patients achieved sufficient tolerability and short-term weight reduction [206-208]. An instant improvement of binge-eating behavior in patients with childhood craniopharyngioma immediately after laparoscopic adjustable gastric banding (LAGB) was observed, but failed in long-term weight reduction. Nevertheless, obesity prevention intervention could be achieved during regular follow-up monitoring [209].

In a systematic review and meta-analysis of the literature, Bretault *et al.* [210] analyzed the 12- month outcome after bariatric surgery for hypothalamic obesity due to craniopharyngioma treatment. At one yr, 6 of 18 cases with follow-up data had lost more than 20% of their initial weight; all had undergone either Roux Y gastric bypass (n=3), sleeve gastrectomy, (n=2) or biliopancreatic diversion (n=1). All patients who had lost less than 5% of their initial weight had undergone LAGB, except one Roux Y gastric bypass case. These findings indicate that Roux Y gastric bypass, sleeve gastrectomy, and biliopancreatic diversion are the most efficient bariatric procedures for weight reduction in hypothalamic obesity of

26

childhood craniopharyngioma patients. However, treatment with invasive, non-reversible bariatric methods is controversial in the pediatric population because of medical, ethical, and legal considerations [209, 211, 212].

Despite the availability of the above-mentioned promising therapeutic approaches, it must be emphasized that in the studies published to date no generally accepted (pharmacological or bariatric) therapy for hypothalamic obesity in childhood craniopharyngioma has been shown to be effective in randomized studies [213].

2.11.1.10. Quality of life, neurocognitive outcome and psychosocial functioning

QoL in craniopharyngioma patients can be affected by both the tumor itself and the treatment received. Reports assessing psychosocial and physical functioning show variable results, ranging from excellent in a majority of subjects to impaired function in almost half of the patients [24, 140, 214-217]. The most common areas of difficulty reported include social and emotional functioning, with patients rating their psychosocial status to be lower than their physical health [140]. Other reported challenges included somatic complaints such as reduced mobility, pain, and self-care [52, 140]. Behavioral questionnaires indicate a high rate of psychopathological symptoms, including depression, withdrawal, and anxiety. The most frequent problems in children's everyday functioning include difficulties in learning, inability to control emotions, unsatisfactory peer relationships, and concerns regarding physical appearance and body image [148, 218].

Reported factors associated with worsening quality of survival outcomes as well as neurocognitive and psychosocial functioning include younger age at diagnosis and preoperative functional impairment. Furthermore, tumor characteristics - including larger tumor volume, hypothalamic and 3rd ventricle involvement at presentation - are reported in the literature to complicate both pre- and post-surgical conditions and therefore survival and QoL outcomes in these patients [33, 40, 139, 219]. Treatment strategies have also been implicated with worse outcomes for surgery alone compared to limited surgery followed by irradiation and for multiple operations for tumor recurrence. Endocrine, neurological, and ophthalmological sequelae all adversely affect QoL outcome [24, 52, 136, 137, 140, 214, 215]. Hypothalamic dysfunction has been found to have the most important negative impact on social functioning, physical ability, and body image [140, 155, 215].

Long-term neurocognitive complications following treatment for craniopharyngioma include cognitive problems, particularly those affecting executive function, attention, episodic memory and working memory [140, 148, 218, 220-225]. Özyurt *et al.* [226] observed that childhood craniopharyngioma patients had lower performance scores in tests of memory and executive functioning when compared with normal controls. Performance in executive functions and functional capabilities were negatively associated with the degree of hypothalamic involvement and damage.

Long-term survivors of childhood craniopharyngioma treated primarily with subtotal surgical resection followed by irradiation were also found to have psychological and educational deficits [148]. Neurocognitive deficits include memory disturbances, slower cognitive speed, attention problems, and behavioral instability [148, 218, 220, 222, 223, 227]. While intact intellectual functioning has been reported in up to 82% of patients, visual memory is impaired despite normal visual-spatial abilities [148, 218]. The acquired deficits in higher cognitive processing such as attention problems are considered precursors to poor academic achievement.

Despite over a quarter of century of literature documenting the neurocognitive challenges encountered by individuals treated for craniopharyngioma, intervention efforts have lagged. Recent case studies have examined the efficacy of cognitive rehabilitation for dysexecutive problems and behavioral lability [228, 229]. Taken together, these case studies suggest that cognitive rehabilitation approaches such as goal management therapy and functional behavioral analysis appear to be useful diagnostic and therapeutic options, compensating for cognitive and psychosocial challenges [230].

2.11.1.11. Cerebrovascular morbidity

Radiation-induced vasculopathies are a rare consequence of radiation therapy for craniopharyngioma. In patients irradiated for craniopharyngioma, moyamoya syndrome (a radiation induced cerebrovascular condition predisposing to stroke) has been described [50, 231]. A retrospective estimate was that 27% of 22 patients treated with irradiation and some combination of surgery and intracystic chemotherapy with a median radiation dose of 52.2 Gy developed some type of vasculopathy, only half of which were symptomatic [231]. Although in this study no association was found between age, radiation dose and maximum or mean dose to the internal carotid arteries with the presence of vascular abnormalities, Regine and colleagues reported a 13.7% rate of cerebrovascular events, all in irradiated cases receiving over 61 Gy [232]. No cerebrovascular clinical events have been reported in any other series of conventionally fractionated radiotherapy for craniopharyngioma, including those with large patient

2.11.1.12. Second malignant neoplasms

In the largest reported series, no second malignancies in the irradiated field were observed in 173 irradiated patients with a median follow-up of 12 yrs [51]. Three long-term survivors (2%) died of systemic malignancies with unspecified diagnoses. Overall, only four cases of second malignancies have been reported [50, 78, 88, 238], comprising 2 in-field glioblastomas [78, 238], one in-field glioma with unspecified grade of malignancy [50] and a posterior fossa meningioma [88].

2.11.1.13. Survival and late mortality

Craniopharyngiomas are associated with significant mortality, with reported overall mortality rates three to five times higher than those of the general population [144, 239]. When assessing mortality in patients with craniopharyngioma, the literature indicates that it is important to consider cases in adult- and childhood-onset craniopharyngioma separately. The overall survival rates (which reflect the effect of multiple treatments) described in exclusive children series range from 83–96% at 5-yr [23, 43, 78, 155, 166, 167, 238] and 65-100% at 10-yr [23, 78] [24, 50, 139, 140, 165, 166, 168-171, 238, 240] and average 62% at 20-yr [232]. In adults or a mixed-age range population (adults and children) series, the overall survival rates range from 54-96% at 5-yr [20, 38, 48, 51, 82, 144, 214, 233, 238, 241], from 40-93% at 10-yr [38, 48, 51, 82, 136, 144, 214, 233, 238, 239, 241], and from 66–85% at 20-yr [51, 82, 144] (Table 7). The lower limits of survival rates usually reflected data from earlier series, before modern advances in microsurgery, neuroimaging, and radiotherapy. It is not clear whether the age at diagnosis represents a survival prognostic factor because some studies have shown that the youngest patients have better survival rates [20, 38, 238, 239]; others have found better outcome in older patients [51, 219], whereas still other studies report no difference between pediatric and adult populations [48, 82, 233, 242, 243]. The role of gender as a prognostic factor is not established; some authors report a higher mortality among females [144, 239], but others have not found any gender differences [48, 166, 233, 243]. One of the two studies reporting higher mortality rates in females suggested a possible role of estrogen deficiency [144], but the other study did not consider that unsupplemented gonadal insufficiency had a significant impact on enhanced mortality [239].

Disease related mortality can occur even many yrs after treatment. Causes of late mortality include those directly related to the tumor or its treatment such as progressive disease with multiple recurrences, chronic hypothalamic insufficiency, hormonal deficiencies, cerebrovascular disease and seizures [136, 137, 139, 140, 165]. Other causes have been described, including decreased mineral bone density and non-alcoholic steatohepatitis, leading to liver cirrhosis in some cases [22, 140, 162, 165, 244-248]. A recent review has reported substantial long-term morbidity with hypopituitarism, increased cardiovascular risk, hypothalamic damage, visual and neurological deficits, reduced bone health, and reduction in QoL and cognitive function. The standardized overall mortality rate varies from 2.88 to 9.28 in cohort studies covered in this review. According to the review, craniopharyngioma patients have a 3-to 19-fold higher cardiovascular mortality in comparison to the general population, and female craniopharyngioma patients have an even higher risk [143].

Tumor size is likely to be a prognostic factor because increased survival rates have been shown in tumors with a diameter smaller than 3 cm [242]. The histological type as a prognostic factor is also controversial; better 5-yr survival rates have been found in the squamous epithelial type vs. the adamantinomatous and combined histological types [249]. Higher perioperative deaths have also been reported in adult adamantinomatous tumors [250], but other authors have not found significant differences between the two histological types [251, 252]. Several studies have described a more favorable prognosis when tumors lack calcification, especially in adult craniopharyngioma patients [242, 250], although no specific pathological feature predicted survival in childhood craniopharyngioma patients [167]. In other studies, neither tumor histology [48, 242] nor tumor location [48, 166] had prognostic importance. In childhood craniopharyngioma patients, the use of modern imaging as well as a good initial performance status (measured according to a functional classification that includes the presence of hypopituitarism, visual deficits, and neurological impairment) have been correlated with enhanced overall post-surgical survival at 10-yr [78]. It is not clear whether the presence of hydrocephalus constitutes a prognostic factor because increased mortality [219] and lack of association with mortality have been reported [48, 166, 167, 233, 253].

Sterkenburg *et al.* [254] recently reported that hypothalamic involvement had a significant negative impact on 20-yr overall survival. The degree of surgical resection had no effect on 20-yr progression

28

free survival rate in craniopharyngioma survivors, supporting the concept that gross-total resection was of no advantage in terms of tumor recurrence.

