2.9.2. Proton beam therapy

Proton beams have an "inverse dose profile" across the tissues, whereby the dose released by the particles increases with penetration depth until reaching a maximum at the end of the particle range (Bragg peak). Beyond the Bragg peak, practically no dose is deposited. Fitzek and colleagues published the first series of 15 craniopharyngioma patients treated with combined proton-photon irradiation for residual or recurrent disease [89]. Actuarial 5- and 10-yr local control rates were 93% and 85%, respectively, with 10-yr survival expectancy in 72% of patients. No treatment-related neurocognitive deficits were reported; functional status, academic skills and professional abilities were unaltered after proton beam therapy. Luu and colleagues published a preliminary report in 2006 on 16 patients treated with proton beam therapy [90]. Local tumor control was achieved in 14 of 16 (87.5%) patients. During follow-up (12 to 121 month later), late sequelae included newly diagnosed panhypopituitarism, a cerebrovascular accident and an out-of-proton-field posterior fossa meningioma (59 month following proton beam therapy administered to patient who previously received photon radiotherapy). One study of proton beam therapy in craniopharyngioma assessed cyst growth during the treatment course: 24% of patients demonstrated cyst enlargement and 5% cyst reduction requiring modification of the treatment plan, while one patient required cyst drainage during treatment [88].

Clinical outcome data are still very limited for assessing the value of proton beam therapy compared to modern photon therapy, as the technique is available in only a few centers. However, proton beam therapy has the potential advantages of better conformation of dose to the target volume, sparing of critical structures, reduced integral dose, and lower dose of secondary neutrons, which should reduce the risk of secondary malignancies [91-93]. As proton beam therapy becomes more available, additional data on this promising therapy is expected.

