2.9.3. Stereotactic radiotherapy

Stereotactic radiotherapy (SRT) can be given in a single fraction (stereotactic radiosuergery) or in multiple doses (fractionated stereotactic radiotherapy). SRT permits a highly conformal dose distribution and delivery to the tumor and provide a steep dose gradient to surrounding normal tissue.

SRT is a modality combining the accurate focal dose delivery of stereotactic radiosurgery with the radiobiological advantages of fractionation [83]. It requires sophisticated treatment planning systems, a dedicated high-energy linear accelerator, and stereotactic mobilization devices. Compared with conventional irradiation, it adopts reduced safety margins and offers optimal sparing of the normal tissue surrounding the tumor, thereby possibly minimizing the acute and long-term toxicities of irradiation [75,

94, 95].

The data on the usefulness of SRT for the management of craniopharyngiomas are limited, but the larger series published thus far provide promising results [94, 95]. The median target dose reported was 52.2 Gy with conventional fractionation and a safety margin of 2 mm. The 10-yr actuarial local control and overall survival rates were 100 and 83%, respectively. Side effects included mild acute toxicity and two patients developed initial enlargement of the cystic component, necessitating stereotactic aspiration in one patient. Reported median (4 yrs) follow-ups (7 month to 12 yrs) revealed 16.6% of subjects developed impaired pituitary function; no deterioration of vision, radionecrosis, or second malignancies were observed.

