4.2. Statistical endpoints and independent variables

The present protocol is a prospective, multicenter registry with the goal to observe and analyse multidisciplinary treatment approaches in childhood-onset craniopharyngioma. Therefore, several endpoints were chosen that reflect patients' survival and QoL. The association between these endpoints and a set of independent variables that represent diagnostic characteristics and treatment strategies will be analysed. On the basis of previous analyses (e.g., KRANIOPHARYNGEOM 2000 / KRANIOPHARYNGEOM 2007), the independent variables have been divided into two categories according to their expected influence on outcome and prognosis of childhood-onset craniopharyngioma.

Endpoints: - Overall survival (OS) defined as time from diagnosis to death

- Progression-free survival (PFS) defined as time from diagnosis to progression or death (whichever occurs first)
- Quality of life (PedQol, PedsQL, FMH)
- Degree of obesity (BMI SDS)

Factors of influence (mandatory):

- Tumor location (grade of hypothalamic involvement, grade 0-2)
- Neurosurgical treatment strategy (intended radical resection vs.
- incomplete resection + XRT)
- Realized degree of surgical resection (complete resection vs. incomplete resection)
- Postsurgical hypothalamic lesions (grade 0-2)
- Irradiation: modality (photon vs. proton beam therapy) and treatment (dose)

Factors of influence (potential):

- Clinical manifestations and symptoms in history
- Duration of history
- Histology (adamantinomatous vs. papillary type)
- Hydrocephalus at diagnosis
- Patient load of treating neurosurgical units (based on patient load during 10 yrs)
- Patient load of treating radiotherapy units (based on patient load dring 5 or 10 yrs)
- Tumor structure in imaging (tumor volume, cysts, calcifications)
- Endocrine deficiencies (number of deficient hypothalamic-pituitary axes)
- Growth hormone substitution (patient age at initiation, duration)
- Ophthalmological deficits (visual acuity, perimetric deficits)
- Neuropsychological findings, memory deficits, cognition (HIT-Basisdiagnostikum)

- Eating disorders (IEG)
- Experimental therapeutic approaches for obesity treatment (GLP-1R Agonists, Oxytocin)
- Other experimental therapeutic approaches, e.g. intracavitary therapy (intracystic IFN- α)

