4.3. Statistical analysis

The analysis of the data collected in this registry will be mainly descriptive. All inferential analyses will be regarded as exploratory (hypotheses generating) and will be interpreted accordingly. The aim of the analyses is to describe the frequency and modality of treatment approaches and to investigate their influence on survival and QoL. Since the planned study is a purely observational study, no randomized comparisons of treatment strategies are possible. Therefore, in addition to univariable analyses, multivariable analysis strategies are used to take account of different baseline risks due to different demographic or diagnostic characteristics. The model selection in the mutivariable analyses can be done by clinical considerations or by means of automated selection as likelihood-ratio based stepwise selection procedures.

Continuous variables (e.g., BMI SDS, QoL) will be summarised using the following descriptive statistics: n (non-missing sample size), number of missing values, mean, standard deviation, median, Q25%, Q75%, maximum and minimum. Histograms or boxplots will be used for graphical presentation of data. For the comparison of independent groups, statistical tests appropriate to the statistical distribution of the particular endpoint will be used (e.g., Student's t-test, Mann-Whintey U-test). To assess the difference of measurements between two different time points, statistical tests as Student's t-test for paired samples, Wilcoxon signed-rank test, or the sign-test will be applied. For comparison of more than two successive measurements, methods accounting for intra-individual correlation will be used (e.g., Linear Mixed Models), additionally adjusting for potential confounders.

Time-to-event endpoints as OS and PFS will be analysed descriptively using the Kaplan-Meier method. Groups will be compared using the log-rank test. Multivariable analyses will be performed using Cox proportional hazard regression analysis.

For categorical variables, the frequency and percentages (based on the non-missing sample size) of observed levels will be reported. Bar charts will be used for graphical presentation of data. The association of a categorical outcome and categorical independent variables will be analyszed using Fishr's exact test or the χ^2 test.

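### PFS is the only registry endpoint that reflects tumour control, and deaths without progression can dilute or distort what it says about recurrence

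*Protocol*

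**What the plan says.** Section 4.2 lists four endpoints: OS, PFS, quality of life and BMI SDS. Two are time-to-event endpoints: "Overall survival (OS) defined as time from diagnosis to death" and "Progression-free survival (PFS) defined as time from diagnosis to progression or death (whichever occurs first". Death is not restricted by cause. A death after progression is not a PFS event, because the first event ends the observation.

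The mandatory factors include "Realized degree of surgical resection (complete resection vs. incomplete resection", together with surgical strategy, postsurgical hypothalamic lesions and irradiation modality. For OS and PFS, section 4.3 plans Kaplan-Meier curves, then "Groups will be compared using the log-rank test", then Cox regression. All inference is exploratory. No analysis of progression on its own, or with death as a competing event, is named.

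On late death, section 2.11.1.13 names progressive disease as one cause, and also "chronic hypothalamic insufficiency, hormonal deficiencies, cerebrovascular disease and seizures", liver cirrhosis, and cardiovascular mortality raised 3- to 19-fold. It gives an average 20-year survival of 62% in children's series. The same section summarises one cited study in which degree of resection had no effect on the 20-year progression- "free survival rate in craniopharyngioma survivors, supporting the concept that gross-total resection was of no advantage in terms of tumor recurrence".

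**The concern.** Tumour control weighed against sequelae is the central treatment question of this registry, and PFS is the only endpoint that speaks to the first half of it. A PFS hazard ratio mixes two things: the effect on progression and the effect on death without progression.

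The protocol makes it plausible that the second differs between resection groups, in either direction. Section 2.11.1.3 reports a marked rise in hypothalamic dysfunction after radical surgery, which could add late deaths in the complete-resection group. Section 2.11.1.13 links hypothalamic involvement to worse 20-year survival, and section 3.1 says complete resection should be avoided in such tumours, which could put the excess in the incomplete-resection group. No death rate by resection group is given, so the direction of any distortion cannot be predicted.

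The horizon is also long. The protocol's opening statement keeps patients from the earlier studies under follow-up, so late deaths will accumulate.

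**Working it through.** The protocol states no event count, power or effect size, so there is no figure to reproduce. The check asks how far the PFS hazard ratio can depart from the progression hazard ratio at rates the protocol itself reports.

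**Inputs**
- Progression: 21% after incomplete resection plus radiotherapy, 71% to 90% after incomplete resection alone (section 2.8.1.1). No horizon is given; 10 years is assumed. With h = -ln(1 - p)/10, h = 0.0236, 0.1238 and 0.2303 per year for 21%, 71% and 90%.
- Death: 87% survival at 10 years (section 2.3) gives -ln(0.87)/10 = 0.0139 per year. 62% at 20 years (section 2.11.1.13) gives -ln(0.62)/20 = 0.0239 per year.
- The share of deaths unrelated to tumour is not given. The hazard d of death without progression is therefore set at 0.0070 (half of 0.0139), 0.0139 and 0.0239. The last two treat every death as non-tumour, which is a worst case.
- True progression hazard ratio 0.70 and constant hazards (assumed).

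**Equal death in both groups.** PFS HR = (0.70h + d)/(h + d), for d = 0.0070, 0.0139 and 0.0239:
- 21% progression: 0.77, 0.81, 0.85. For example (0.0165 + 0.0139)/(0.0236 + 0.0139) = 0.81.
- 71% progression: 0.72, 0.73, 0.75.
- 90% progression: 0.71, 0.72, 0.73.
- If the horizon were 20 years, h = 0.0118 for 21% and 0.0619 for 71%, giving 0.81, 0.86, 0.90 and 0.73, 0.76, 0.78.
- If the true progression HR is 1, the PFS HR is (h + d)/(h + d) = 1. Equal death creates nothing.

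As a scale only, the Schoenfeld formula (two-sided 5%, 80% power, 1:1, all assumed) requires 247 progression events for HR 0.70. It requires 453, 719 or 1,207 PFS events for the three diluted values at 21% progression. Deaths do add events: with d = 0.0139 by a factor of (0.0236 + 0.0139)/0.0236 = 1.59 in one group and (0.0165 + 0.0139)/0.0165 = 1.84 in the other. That is less than 719/247 = 2.9.

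**Unequal death, full masking of HR 0.70.** This needs extra d = 0.30h in the group with better control, against a reference of 0.0070:
- 21% progression: extra 0.0071 per year, a ratio of 2.0. Both groups then have 20-year PFS of exp(-0.0305 × 20) = 54%, while cumulative incidence of progression is (0.0236/0.0305) × 0.457 = 35% against (0.0165/0.0305) × 0.457 = 25%.
- 71% progression: extra 0.0371 per year, a ratio of 6.3.

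**Unequal death, imitation.** With equal progression and a doubled death hazard, PFS HR = (h + 2d)/(h + d):
- 21% progression: 1.23, 1.37, 1.50.
- 71% progression: 1.05, 1.10, 1.16.

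**Share of 20-year deaths that PFS counts**, with the same d before and after progression: [d/(h + d)] × [1 - exp(-20(h + d))] / [1 - exp(-20d)]. For d = 0.0139 and 0.0239 this is about 81% at 21% progression, 39% to 40% at 71% and 23% to 25% at 90%.

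**The case against.** The strongest reply is that nothing here is wrong. Progression or death is a standard definition, all inference is exploratory, no decision hangs on PFS, and a competing-risk analysis may sit in a statistical analysis plan that is not at hand. All of this stands, and it limits the weight of the point.

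A second reply is that OS guards against misreading. In the masking case above, if death hazards are the same before and after progression, 20-year OS would be 87.0% against 75.5%. Equal PFS beside unequal OS would alert a careful reader. But it would not give the size of the recurrence difference, and OS also contains deaths after progression. Covariate adjustment in the Cox model does not separate the two components either.

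Three stronger readings are tempting, and the documents do not support them.
- A reader might infer that PFS counts every late death. It counts only deaths with no earlier progression.
- A reader might infer from section 2.11.1.13 that the protocol contradicts itself or will read registry PFS as recurrence. That sentence is background on one cited study whose PFS definition is not given, and sections 4.2 and 4.3 set no such rule. It only illustrates how the reading arises.
- A reader might size the problem from two cited series: "The 10-yr actuarial local control and overall survival rates were 100 and 83%, respectively" (section 2.9.3) and "Actuarial 5- and 10-yr local control rates were 93% and 85%, respectively, with 10-yr survival expectancy in 72% of patients" (section 2.9.2). PFS cannot exceed OS, which suggests gaps of 100 - 83 = 17 and 85 - 72 = 13 points. But both are single irradiated series with no resection comparison and no stated causes of death. The first has a median follow-up of 4 years. The second has 15 patients (13 points is about two) treated for residual or recurrent disease, so some had already progressed under the registry's definition, which runs from diagnosis.

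**Conclusion.** The point holds as an improvement worth making. Neither PFS nor OS, analysed as section 4.3 plans, can isolate progression, and the protocol describes enough late non-tumour mortality for this to matter in some comparisons.

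The size depends on how common progression is. At about 21%, a true progression hazard ratio of 0.70 appears as 0.77 to 0.85 with equal death rates, and a roughly two-fold non-tumour death hazard in the better-controlled group (reference 0.0070 per year) would hide it. At 71% to 90% the dilution is slight (0.71 to 0.75), and hiding the difference at 71% would need a 6.3-fold death hazard.

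These figures rest on constant hazards, a 10-year horizon for the progression rates, and an unknown non-tumour share of deaths, with all deaths taken as non-tumour at the upper end. Full masking or imitation requires unequal death rates, which the documents make plausible in either direction but never quantify. It cannot be said that any resection effect has been or will be hidden.

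**What to change.** Keep PFS and OS as defined. In sections 4.2 and 4.3 add the cumulative incidence of progression, with death without progression as the competing event (Aalen-Johansen estimator), and cause-specific Cox models for each of the two events. State that conclusions about recurrence by degree of resection, surgical strategy or beam modality rest on this analysis and not on PFS.

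The cost is a few sentences and one more exploratory analysis to report and interpret. New data should not be needed, since CRF 6 (section 5) covers status, relapse and death. The form itself is not shown, so it should be confirmed that it records the dates of first progression and of death.
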